Non Amgen Non-investigational Products: Subjects will continue to use stable background lipid lowering therapies as prescribed. These therapies will not be provided by Amgen unless required by law.

Procedures: Subjects who have completed Study 20120123 (and did not experience a treatment-related serious adverse event) and have signed parental/guardian consent/permission and subject consent/assent for Study 20120124, will be enrolled. Subjects with HoFH being considered for participation in this study, and who have signed parental/guardian consent/permission and subject consent/assent, will be assessed for inclusion and exclusion criteria. Medical and medication history will be obtained. Subjects will undergo screening laboratory assessments, including a SC administration of placebo to evaluate tolerability of the SC injection in subjects with HoFH only. Lipid eligibility screening must be conducted after subject has been on a low-fat diet and receiving stable lipid-lowering therapy for ≥ 4 weeks. Subjects should maintain their diet, lipid-lowering therapy, and exercise regimen throughout screening and all phases of study participation. Eligible subjects will start receiving open-label evolocumab, in addition to their background lipid-lowering therapy.

Day 1 is defined as the day of first administration of evolocumab. Subsequent study visits are at weeks 4, 12, 24, 36, 48, 60, 72, and 80 (EOS, end-of-study). Subjects who discontinue IP early for any reason will be asked to continue to return for all other study procedures and measurements until the end of the study.

Adverse Events/Serious Adverse Events/Adverse Device Effects (ADE) and concomitant therapy will be collected at every study visit. Other assessments and procedures are done as per Schedule of Assessments ([Table 2](#)) and include vital signs, dietary instruction, physical exam,

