9.2 Safety Event Reporting Procedures

9.2.1 Adverse Events

9.2.1.1 Reporting Procedures for All Adverse Events (Serious or Non-serious Adverse Events)

Refer to [Sections 9.2.1.2](#) and [9.2.1.3](#) for additional information regarding the reporting of serious adverse events.

For subjects enrolling in Study 20120124 after completion of Study 20120123 (HeFH subjects) the investigator is responsible for ensuring that all adverse events and all adverse device effects observed by the investigator or reported by the subject that occur after the first dose of investigational product/study treatment/protocol-required therapies through the end of Study 20120124 are reported using the Event CRF.

For subjects not rolling over from Study 20120123 (HoFH subjects), the investigator is responsible for ensuring that all adverse events possibly related to study procedures, adverse device effects, and serious adverse events are reported from signing of the ICF. All other adverse events are reported that occur after enrollment. The investigator is responsible for ensuring that all adverse events observed by the investigator or reported by the subject that occur from signing of the ICF or that occur after enrollment through the end of Study 20120124 are reported using the Event CRF.

The investigator must assign the following adverse event attributes:

- adverse event diagnosis or syndrome(s), if known (if not known, signs or symptoms),
- dates of onset and resolution (if resolved),
- severity,
- assessment of relatedness to investigational product (evolocumab and/or the device[s]: the prefilled AI/Pen or AMD), or other protocol-required therapies, protocol-required procedure or activity, and
- action taken.

The adverse event grading scale used will be the National Cancer Institute (NCI) Common Terminology Criteria for Adverse Events (CTCAE). The grading scale used in this study is referenced in [Appendix A](#).

If the severity of an adverse event worsens from the date of onset to the date of resolution, record a single event for each increased level of severity on the Adverse Event Summary CRF.

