9.2.1.2 Reporting Procedures for Serious Adverse Events

The investigator is responsible for ensuring that all serious adverse events observed by the investigator or reported by the subject that occur after signing of the informed consent through 30 days after the last dose of IP or EOS, whichever is later, are recorded in the subject’s medical record and are submitted to Amgen. All serious adverse events must be submitted to Amgen within 24 hours following the investigator’s knowledge of the event via the Event CRF.

If the electronic data capture (EDC) system is unavailable to the site staff to report the serious adverse event, the information is to be reported to Amgen via an electronic Serious Adverse Event (eSAE) Contingency Report Form within 24 hours of the investigator’s knowledge of the event. See [Appendix B](#) for a sample of the eSAE Contingency Report Form. For EDC studies where the first notification of a serious adverse event is reported to Amgen via the eSAE Contingency Report Form, the data must be entered into the EDC system when the system is again available.

The investigator must assess whether the serious adverse event is possibly related to IMP (evolocumab). This relationship is indicated by a “yes” or “no” response to the question: Is there a reasonable possibility that the event may have been caused by evolocumab (investigational medicinal product)? The investigator must assess whether the serious adverse event is possibly related to the prefilled AI/Pen or the AMD (investigational device[s] used to administer evolocumab). The relationship is indicated by a “yes” or “no” response to the question: Is there a reasonable possibility that the event may have been caused by the investigational device(s)? Relatedness means that there are facts or reasons to support a relationship between IP and the event.

The investigator must assess whether the serious adverse event is possibly related to any study-mandated activity or procedure. This relationship is indicated by a “yes” or “no” response to the question: “Is there a reasonable possibility that the event may have been caused by a study activity or procedure”?

The investigator is expected to follow reported serious adverse events until stabilization or reversibility.

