9.3 Pregnancy and Lactation Reporting

If a pregnancy occurs in a female subject, or female partner of a male subject, while the subject is taking evolocumab report the pregnancy to Amgen as specified below.

In addition to reporting any pregnancies occurring during the study, investigators should monitor for pregnancies that occur through 15 weeks after the last dose of evolocumab.

The pregnancy should be reported to Amgen Global Patient Safety within 24 hours of the investigator's knowledge of the event of a pregnancy. Report a pregnancy on the Pregnancy Notification Worksheet ([Appendix C](#)). Amgen Global Patient Safety will follow-up with the investigator regarding additional information that may be requested.

If a female subject becomes pregnant during the study, the investigator should attempt to obtain information regarding the birth outcome and health of the infant. If a male subject's female partner becomes pregnant, the investigator should discuss obtaining information regarding the birth outcome and health of the infant from the pregnant partner.

Any termination of the pregnancy will be reported to Amgen Global Patient Safety regardless of fetal status (presence or absence of anomalies) or indication for procedure.

If the outcome of the pregnancy meets a criterion for immediate classification as a serious adverse event (eg, female subject experiences a spontaneous abortion, stillbirth,

Approved

or neonatal death or there is a fetal or neonatal congenital anomaly) the investigator will report the event as a serious adverse event.

If a female subject breastfeeds while taking evolocumab, report the lactation case to Amgen as specified below.

In addition to reporting a lactation case during the study, investigators should monitor for lactation cases that occur through 15 weeks after the last dose of evolocumab.

Any lactation case should be reported to Amgen Global Patient Safety within 24 hours of the investigator's knowledge of event. Report a lactation case on the Lactation Notification Worksheet ([Appendix C](#)). Amgen Global Patient Safety will follow-up with the investigator regarding additional information that may be requested.

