5.1 Study Timepoints

Enrollment Date

The enrollment date is defined as the date collected on the Subject Enrollment eCRF.

Study Day 1

For each subject, Study Day 1 is defined as the first day of investigational product administration. If a subject never received IP, then Study Day 1 is defined as the date of enrollment.

Study Day

For each subject, and for a given date of interest, study day is defined as the number of days since Study Day 1:

Study day = (date of interest – Study Day 1 date) + 1.

If the date of interest is prior to the Study Day 1:

Study day = (date of interest – Study Day 1 date), so that the day prior to Study Day 1 is study day -1.

First Dose Date of Investigational Product

For each subject, the First Dose Date of Investigational Product is defined as the first administration date of the IP as recorded on the IP administration eCRF.

Last Dose Date of Investigational Product

For each subject, the Last Dose Date of Investigational Product is defined as the date of the last administration of the IP:

If the last dose was administered in-clinic, then the Last IP Dose Date is the last start date captured on the IP Administration (In-Clinic) eCRF page.

If the last dose was administered at a non-investigator site location, then the Last IP Dose Date is defined as the final dose date reported by the subject on the Non-Clinic Final Investigational Product Dose Date eCRF page.

End of Study (EOS) Date for Each Subject

End of study for each subject is defined as the last day on which the enrolled subject in this study completes the end-of-study visit (week 80) or terminates the study early. The date will be recorded on the End of Study eCRF page.

Study End Date for the Overall Study

The study end date is defined as the date when the last enrolled subject has completed the end-of-study visit (week 80) (ie, last subject last visit).

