“Did event start before first dose of investigational product” equal to No or missing on the Events eCRF and up to and including 30 days after the last dose of investigational product or the EOS date or the data cutoff date, whichever is earlier for interim analysis. For primary analysis, treatment emergent adverse events are events categorized as Adverse Events (AEs) starting on or after first dose of investigational product as determined by “Did event start before first dose of investigational product” equal to No or missing on the Events eCRF and up to and including 30 days after the last dose of investigational product or the EOS date, whichever is earlier. Any AE that cannot be defined clearly as a TEAE will be considered a TEAE in the database.

Reflexive Approach for LDL-C and VLDL-C

For all analyses related to LDL-C and VLDL-C, unless specified otherwise, the following reflexive approach will be used. When calculated LDL-C is less than 40 mg/dL or triglycerides > 400 mg/dL, the UC LDL-C value from the same blood sample will be used instead of calculated LDL-C and the UC VLDL-C value from the same blood sample will be used instead of calculated VLDL-C, if available.

6. Analysis Sets

The full analysis set (FAS) includes all subjects with HeFH from parent study 20120123 who are enrolled **and dosed** and all subjects with HoFH who are enrolled and dosed in this study.

Unless specified otherwise, the FAS will be the default analysis set in this study.

7. Planned Analyses

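### The treatment-emergent window closes before the protocol's event collection does, and no planned table is sure to show what falls outside it

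*SAP*

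**What the plan says.** The primary endpoint is treatment-emergent adverse events (TEAEs) at week 80 (protocol 10.1.1.1). The protocol sets no window for what counts as treatment-emergent; only SAP 5.3 does. For the primary analysis the event must start on or after first dose and "up to and including 30 days after the last dose of investigational product or the EOS date, whichever is earlier". The interim version adds a third limit: "30 days after the last dose of investigational product or the EOS date or the data cutoff date, whichever is earlier for interim analysis". An event that cannot be clearly classified is counted as a TEAE.

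Collection runs longer:
- Protocol 9.2.1.1: in both cohorts, adverse events occurring "through the end of Study 20120124 are reported using the Event CRF".
- Protocol 9.2.1.2: serious events are reportable if they are ones "that occur after signing of the informed consent through 30 days after the last dose of IP or EOS, whichever is later".
- Protocol synopsis, Procedures: "Subjects who discontinue IP early for any reason will be asked to continue to return for all other study procedures and measurements". Section 6.2.2 says the same of a subject who cannot tolerate the dose.

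SAP 5.1 fixes a subject's EOS date: "End of study for each subject is defined as the last day on which the enrolled subject in this study completes the end-of-study visit", or the day of early termination.

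SAP 9.6.1 summarises subject incidence of TEAEs. SAP 9.6.2 then lists tables of TEAEs, serious events, events leading to withdrawal of drug, and fatal events. The treatment-emergent qualifier is attached only to the first. No window is given for the others, and no summary of all collected events is planned.

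**The concern.** One document uses the earlier of two dates and the other uses the later, so some events are collected under the protocol but fall outside the primary endpoint. Two groups are involved: subjects who leave the study soon after a dose, and subjects who stop drug but keep attending visits. The second group matters for a tolerability question, because some of them will have stopped for intolerance and the protocol deliberately keeps following them.

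The SAP's other safety windows are not tied to last dose. Appendix A assigns week-80 CK and chemistry results up to EOS whether or not the subject is still on drug. An off-drug enzyme abnormality at week 80 can therefore count in a secondary safety endpoint, while an adverse event starting the same day in the same subject cannot count in the primary one. In a single-arm paediatric study of about 124 subjects, a reader of the report should be able to see what happened after stopping.

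**Working it through.** **Inputs**
- Study day of a scheduled visit = 7 × week + 1 (SAP Appendix A).
- TEAE window closes at min(last dose + 30, EOS) (SAP 5.3).
- Adverse event collection closes at EOS (protocol 9.2.1.1, reading the end of the study as the subject's own EOS).
- Serious event collection closes at max(last dose + 30, EOS) (protocol 9.2.1.2).
- Dosing is every 4 weeks with none at week 80 (protocol glossary and Table 2), so the last planned dose is inferred to be week 76, day 7 × 76 + 1 = 533.

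**The plan's own figure.** Week 80 is day 7 × 80 + 1 = 561, the target day in Appendix A.

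**(a) Serious events after EOS but within 30 days of last dose**
- Subject leaving d days after last dose, d < 30: days outside = 30 − d. This gives 30 for d = 0, 29 for d = 1, 16 for d = 14 and 2 for d = 28.
- On-schedule completer: 533 + 30 = 563 against EOS on day 561, so 2 days outside. If the visit is a week early (day 554), 563 − 554 = 9 days.
- If the visit is a week late (day 568), the order reverses: the window closes at day 563, and 568 − 563 = 5 days of all adverse events fall outside.

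**(b) Subject stops drug and stays to day 561.** Days outside = 561 − (last dose day + 30).

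| Last dose | Day | Window closes | Collected days outside |
|---|---|---|---|
| Day 1 only | 1 | 31 | 530 |
| Week 12 | 85 | 115 | 446 |
| Week 20 | 141 | 171 | 390 (55.7 weeks) |
| Week 24 | 169 | 199 | 362 |
| Week 48 | 337 | 367 | 194 |
| Week 72 | 505 | 535 | 26 |

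These figures assume full follow-up to week 80. Protocol 8.1 allows a lesser level after stopping, so they are upper limits for each stopping day.

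**Scale under an assumption.** The documents do not say how many subjects will stop drug and stay. Suppose 2% to 20% of 124 do (2.5 to 24.8 subjects), with last doses spread evenly from the day 1 dose to the week 72 dose. The mean is (530 + 26) / 2 = 278 days outside per such subject, or about 690 to 6,900 person-days. Against planned follow-up of 124 × 561 = 69,564 person-days, that is 1% to 10%. This measures observation time, not events or incidence.

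**Does another parsing remove it?** SAP 5.3 could be read as 30 days after the earlier of last dose or EOS. That closes gap (a) but leaves (b) unchanged. The interim sentence, which adds the data cutoff to the same list, and the minimum-of-dates exposure formulas in SAP 5.3 both favour the reading used here.

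**The case against.** The strongest reply is that nothing is contradicted. The protocol says how long sites report; the SAP says which onsets count as treatment-emergent. Last dose + 30 days is an ordinary on-treatment window, sits close to the SAP's exposure rule of last dose + 28 days, and uses the protocol's own general post-dose figure of 30 days. That stands, and it is why the main table should not change.

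Four stronger inferences are tempting but not supported:
- *Unresolved harm is dropped.* The SAP rule is about onset. An event starting inside the window counts however long it lasts, and protocol 9.2.1.1 requires follow-up to stabilization or reversibility. One narrow exception remains: the same section records a separate event for each rise in severity, so a late worsening may carry a late date.
- *The 15-week figure shows that 30 days is too short.* Protocol 9.3 says "investigators should monitor for pregnancies that occur through 15 weeks after the last dose of evolocumab" and treats lactation likewise; the contraception rule uses the same period. No section makes it a general adverse event risk period.
- *Late serious and fatal events vanish from the report.* SAP 9.6.2 does not restrict those tables to treatment-emergent events, and protocol 10.4.2 also lists them separately. They may well appear. The fault is that the window is unstated.
- *Days outside the window measure bias.* The summary is subject incidence. Overall incidence changes only if a subject's first event falls outside the window; term-level counts change only for terms new to that subject.

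It is also fair to say that off-drug events in a study with no concurrent control are hard to interpret. That is a reason to label them, not to leave them unreported. The SAP's fallback for unclear events does not help, since it does not reach an event clearly dated after the window.

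**Conclusion.** The point holds as a mismatch between collection and analysis; severity is minor. Serious events after EOS but within 30 days of last dose must be reported yet cannot be treatment-emergent. The gap is up to 30 days for early leavers and about 2 days for on-schedule completers. In subjects who stop drug and stay, events starting more than 30 days after last dose are collected but lie outside the primary endpoint: 390 days if the last dose is day 141, with a range of 530 to 26 days across stopping points up to week 72. No planned table is guaranteed to show the non-serious ones, and the window for the serious and fatal tables is left open.

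The cut can lower reported incidence and cannot raise it. A reader might infer that tolerability will be materially overstated, but the documents give neither a stopping rate nor an off-drug event rate, so no amount can be put on it. The day counts rest on the inferred week 76 last dose, on EOS at day 561 unless stated, and on full follow-up after stopping.

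**What to change.** Leave the TEAE definition and the main table as they are. In SAP 9.6.2:
1. State that the serious and fatal event tables include every event from first dose through the later of last dose + 30 days or EOS, to match protocol 9.2.1.2. With that end date, the days outside fall to 0 for these tables in every case above.
2. Add one supplementary summary of all collected adverse and serious adverse events from first dose to the end of protocol collection.
3. Add a listing of events starting more than 30 days after last dose, with days since last dose.

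The cost is a few lines of SAP text, one table and one listing, all from data already collected. The downside is that the supplementary outputs will include off-drug background events with no concurrent control, so they should be labelled that way and set beside the TEAE table rather than in place of it.

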7.1 Data Monitoring Committee (DMC)

An external independent DMC has been established to formally review the accumulating data from this study to ensure there is no avoidable increased risk for harm to subjects. The independent DMC is chaired by an external academic cardiologist who is an expert in lipids and clinical trials. Details are provided in the DMC charter.

7.2 Interim Analysis and Early Stopping Guidelines

The interim analysis will be conducted when all the enrolled subjects in the study have opportunity to experience 28 weeks of investigation product exposure or have early terminated from the study. At that time, the database related to the interim analyses of the study will be cleaned, processed and a snapshot will be taken. Unless specified otherwise, the FAS will be the default analysis set in this

study. Similar to the primary analysis, the interim data will be summarized by cohort (HeFH and HoFH). Statistical analysis in this interim analysis is descriptive in nature for all safety and efficacy endpoints if applicable. No statistical hypotheses testing or missing value imputation is planned. There is no study stopping rule for either futility or efficacy and the current design or execution of the study will continue without any changes regardless of the result of the interim analysis.

7.3 Primary Analysis

To evaluate the safety, tolerability and effect of 80 weeks of SC evolocumab when added to standard of care in pediatric subjects 10 to 17 years of age with HeFH or HoFH, the primary analysis will be conducted when all the enrolled subjects in the study have either completed all the scheduled visits up to and including week 80 or have early terminated from the study. At the time of the primary analysis, the database will be cleaned, processed and locked. Unless specified otherwise, the FAS will be the default analysis set in this study and data will be summarized by cohort (HeFH and HoFH) **as well as by the randomized treatment group of the parent study for HeFH cohort (as defined in [section 5.3](#))**. All analyses will include estimation for all the endpoints. No formal hypotheses will be tested in this study.

7.4 Final Analysis

Not applicable.

8. Data Screening and Acceptance

8.1 General Principles

The objective of the data screening is to assess the quantity, quality, and statistical characteristics of the data relative to the requirements of the planned analyses.

8.2 Data Handling and Electronic Transfer of Data

The Amgen Global Study Operations-Data Management (GSO-DM) department will provide all data to be used in the planned analyses. This study will use the RAVE database.

All data collected in the eCRF will be extracted from RAVE. Protocol deviations will be transferred from eClinical. Final PK data will be transferred from statistical programming to Amgen's PKDM group. Details on data transfer will be provided in the Data Transfer Plan.

